Secondary Hypothesis: We hypothesize that the TV generated via PLV in the immediate neonatal transition phase will be highly variable.

PHASE II:

Primary Hypothesis: We hypothesize that real time PiP adjustments are feasible when utilizing a T-Piece resuscitator to provide VTV for goal TV of 4-6ml/kg that can be seamlessly transitioned in the NICU.

Secondary Hypothesis:

- i. We hypothesize that infants receiving VTV will require lower PiP, will have lower oxygen needs with improved long term pulmonary morbidities
- ii. We hypothesize that VTV will have lower complication rates as compared to PLV.

SPECIFIC AIMS:

PHASE I:

Specific Aim #1: To assess feasibility of measuring TV in the DR for preterm infants <32 weeks with need for invasive positive pressure ventilation via endotracheal tube (ETT).

Objectives:

Date 10/15/2018
Protocol Version-I

- To assess the % infants with all equipment ready(including NM3 monitor and flow sensor) in DR to measure TV
- To assess the % infants where TV was measured within 60 seconds of ETT placement and positive pressure ventilation initiation.

Specific Aim #2: To assess variability in delivered TV in the DR with PLV for preterm infants <32 weeks with need for invasive positive pressure ventilation via ETT

Objectives:

- To assess the % infants with tidal within goal of 4-6ml/kg via routine PLV
- To assess the % infants with under or over ventilation using routine PLV
- To assess changes in TV with administration of surfactant with the same pressures

PHASE II:

Specific Aim #1: To assess feasibility of providing VTV, by quickly adjusting the peak inspiratory pressures (PiP) provided via the T-Piece resuscitator based on real time TV measurements.

Objectives:

- To assess the recruitment rates and successful enrollment into the study
- To assess the % of infants with measurable TV and successful adjustment of PiP to reach goal TV
- To assess the % of infants who fail VTV and need to be switched to conventional PLV

Specific Aims #2: To compare the pulmonary mechanics and physiology during VTV, respiratory support requirements

Objectives:

- To compare TV delivered during PLV versus VTV.
- To compare FiO2 requirement during PLV versus VTV
- Evaluate PiP, mean airway pressures (Paw), peak end expiratory pressures (PEEP) and oxygen requirement during the first 48 hours between the two study arms.
- Evaluate differences in blood gas results (pH, PCO2 levels).

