- The DR staff including the attending neonatologists, advanced practitioners and respiratory therapists will be trained and will have ample time to feel comfortable about the flow sensor and the Respirationics device prior to starting the study. Our staff currently uses a similar flow sensor device in the NICU and thus we do not anticipate any significant issues pertaining to training.

Subject stopping rules:

- Development of pneumothorax, pneumomediastinum
- PiP requirement >30 cm H₂O pressure for more than 60s
- Persistent low saturation or bradycardia with 60 seconds of optimum VTV

Individual responsible for stopping/modifying the protocol: **[name], MD**, Interim Division Chief along with the IRB will serve as the Safety Monitor for the study. Any SAEs will be reported to the IRB within 48 hours of occurrence.

POTENTIAL PITFALLS AND ALTERNATIVES

Inability to measure small tidal volume: As the *Respironics NM3 monitor* has never been tested to measure TVs in the range of 2-3ml/breath, we potentially run the risk of inability to measure the TV in this range in the extremely low birth weight infants (<500gm). We do plan to measure the TV in a standard test lung after acquisition of the device to ensure accuracy. Alternatively, we may have use the *Dräger Babylog VN500 ventilator* with a flow sensor device to measure TV in the DR. This will be more challenging as having a ventilator in the DR, but is possible to have one stand by, only to measure the TV from its circuit.

Leak from the ETT: Presence of a large leak may pose a significant problem in clinical situations as it makes accurate estimation of TV difficult. We will strictly adhere to the NRP guidelines for endotracheal tube sizes according the patients weight and gestational age and will evaluate both inspiratory and expiratory TV for the study. In situations with a large leak (>50%), we will use the expiratory TV as the marker for delivered TV.

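### Does the 50% leak rule for delivered tidal volume undermine the counts against the 4-6 mL/kg goal?

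*Combined protocol and SAP*

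**What the plan says.** The rule is in Potential Pitfalls and Alternatives, under Leak from the ETT. That paragraph accepts that a large leak makes tidal volume (TV) hard to estimate, commits to NRP tube sizing, and states that the team "will evaluate both inspiratory and expiratory TV for the study". It then gives its one scoring rule: "In situations with a large leak (>50%), we will use the expiratory TV as the marker for delivered TV". How percentage leak is calculated, which signal counts at 50% or less, and why 50% was chosen are not stated.

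Five objectives under Specific Aims use the recorded volume:

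- Phase I Aim 2 has three. The first is "To assess the % infants with tidal within goal of 4-6ml/kg via routine PLV". The second counts the infants who fall below or above that range, and the third looks at how TV shifts after surfactant when pressures are left unchanged.
- Phase II Aim 1 has one: "To assess the % of infants with measurable TV and successful adjustment of PiP to reach goal TV".
- Phase II Aim 2 has one: "To compare TV delivered during PLV versus VTV".

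The Phase II primary hypothesis also refers to the goal: "real time PiP adjustments are feasible when utilizing a T-Piece resuscitator to provide VTV for goal TV of 4-6ml/kg".

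Under Primary Outcome Variable, Phase I is judged on whether TV is measured within 60 seconds and Phase II on the timing of VTV initiation. Data Analysis sets feasibility at 80% of infants measured in time and plans descriptive summaries without hypothesis tests.

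**The concern.** The goal range is narrow, so even a moderate leak can put a breath in goal on one signal and out of goal on the other. A rule that starts only above 50% leak seems to come too late. With leak taken relative to inspired volume, the two signals can no longer both be in goal once leak passes 33.3%, and from there to 50% the plan does not say which one counts.

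TV is also recorded breath by breath while several objectives count infants, and no rule is given for turning breaths into an infant's category.

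At stake would be the in-goal and out-of-goal percentages in Phase I, the share of Phase II infants brought to goal, and the TV summaries that may help size a later trial. With so few infants, a choice of signal made after seeing the data could move these visibly.

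**Working it through.** **Inputs.** Goal 4-6 mL/kg (Specific Aims; Intervention). Cut-off 50% (Leak from the ETT). Ten infants in Phase I and 15 per arm in Phase II (Sample Size). The leak formula is not in the documents, so two are assumed, with TVi inspired and TVe expired volume:

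- A: L = (TVi - TVe)/TVi, so r = TVi/TVe = 1/(1 - L)
- B: L = (TVi - TVe)/TVe, so r = 1 + L

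**1. The plan's own figure.** Innovation converts the goal for a 500 g infant to 2-3 mL per breath: 0.5 × 4 = 2.0 and 0.5 × 6 = 3.0. This agrees. No derivation of 50% is given, so there is none to reproduce.

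**2. Largest leak with both signals in goal.** This needs TVi ≤ 6 and TVe ≥ 4, so r ≤ 6/4 = 1.5.

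- A: L = 1 - 1/1.5 = 33.3%. At L = 50%, r = 2.0.
- B: L = 1.5 - 1 = 50%, which is exactly the plan's cut-off.

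**3. Part of the inspired goal range that is also in goal on expired volume,** max(0, 6 - 4r)/2:

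| Leak | A | B |
|---|---|---|
| 10% | 78% | 80% |
| 20% | 50% | 60% |
| 30% | 14% | 40% |
| 40% | 0% | 20% |
| 50% | 0% | 0% |

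These are parts of the range, not observed frequencies. Disagreement grows steadily from low leak, so 33.3% is only where overlap ends.

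**4. Must the signals disagree between 33.3% and 50% (formula A)?** Take 40% leak, where TVe = 0.6 × TVi:

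| TVi (mL/kg) | TVe (mL/kg) | Inspired | Expired |
|---|---|---|---|
| below 4 (e.g. 3.0) | below 2.4 (1.8) | below goal | below goal |
| 4 to 6 | 2.4 to 3.6 | in goal | below goal |
| 6 to 6.67 | 3.6 to 4 | above goal | below goal |
| 6.67 to 10 | 4 to 6 | above goal | in goal |
| above 10 (e.g. 12) | above 6 (7.2) | above goal | above goal |

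So they need not. Low and high breaths receive the same category from both signals.

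**5. Step at the cut-off.** If inspired volume is used at 50% or less (the natural but unstated reading), then under A a breath with TVi = 8 scores 8 at 50% leak and 8 × 0.49 = 3.92 at 51%.

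**6. Effect per infant.** 1/10 = 10 points in Phase I; 1/15 = 6.7 points per arm in Phase II. The documents give no leak distribution, so the number of infants to multiply by is unknown.

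**7. Which results use the range.** Of the five objectives, the surfactant change and the PLV versus VTV comparison use TV as a quantity and do not refer to 4-6 mL/kg, so the overlap argument does not reach them. Three remain.

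**The case for a change.** The strongest case for changing the plan is that the same words produce two different rules, depending on an unstated formula, and that each reading of the silence at 50% or less is awkward. If expired volume applies throughout, the rule is redundant. If inspired volume applies below the cut-off, a one-point change in leak can turn an over-ventilated breath into an under-ventilated one (8 against 3.92 mL/kg). Data Analysis says Phase I should show that the measures are reliable and valid, and the pilot's estimates are to inform a later trial. A few sentences would settle all of this, and the adjustment protocol mentioned under Intervention is described only for the intervention arm.

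The omissions are real: the leak formula, the marker at 50% or less and the breath-to-infant summary are not written down, and the step at the cut-off follows if inspired volume is used below it.

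The claim that the cut-off conflicts with the goal does not stand. The leak rule addresses how well TV can be measured; it was not set to match the ratio 6/4, and no section asks for a breath to be in goal on both signals. Nor would a stated rule establish which signal is the truth; any single marker used consistently would serve. The missing breath-to-infant summary has nothing to do with leak and would remain at zero leak. Scoring every breath on expired volume also carries a cost of its own: it could judge Phase II infants on a signal that providers were not targeting, since the adjustment protocol is not reproduced in the document.

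**Conclusion.** No change to the plan is needed. The arithmetic is right under its assumption: 33.3% if leak is relative to inspired volume, 50% if relative to expired volume. In the second case the rule meets the goal range exactly. What is left is ordinary missing detail in a descriptive pilot, which an analyst can fill: state the leak calculation used, summarise each infant's breaths, and show the counts on both signals, which the plan already undertakes to evaluate.

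The primary outcomes and the 80% criterion do not depend on the recorded volume. The exposure is confined to descriptive estimates, at 10 points per reclassified infant in Phase I and 6.7 points per arm in Phase II. How many infants that involves cannot be worked out from the documents; with NRP tube sizing planned, it may be none. This conclusion assumes that both signals are recorded as stated and that the report says which one each count uses.
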